The ratio of the incremental costs to the incremental effects is called the incremental cost-effectiveness ratio (ICER) calculated as: $(Cost_N - Cost_C)/(Health effect_N - Health effect_C)a$. This measure reflects the difference in costs per unit of effect. We will calculate ICERs in terms of natural effects (number of packages AB prescribed) and in terms of QALYs, or net benefits (in case of dominated or dominant interventions).

A well-known issue is the presence of missing data related to the different outcome variables (cost data). Different methods exist to handle this. In the current research project, single imputation methods will be used. In this method, the missing data are replaced with a single predicted value (e.g. the adjusted mean value).(33) Sensitivity analyses will be conducted to determine how different input values will impact the outcome.(33)

Decision-analytic model will be used to predict longer-term patient outcomes and complications for patients as well as their economic impact in the 'intervention' arm versus the 'usual care' arm, as well as to investigate the effect of changes in particular parameters (sensitivity analysis). We will use a combination of decision-trees and markov models to follow hypothetical cohorts over time. The main data as input for the model will be the occurrence of hospital admission for serious infection, health outcomes for non-hospitalized patients and reported cost and HRQoL data (obtained from phase 1 and in case needed from published literature). This kind of model allows us to simulate transitions in various health states beyond the duration of the intervention, and as each health state is associated with costs and utilities, to estimate cost-effectiveness ratios. The health effects in this model will be mainly expressed as quality-adjusted life years (QALYs). QALYs are calculated by multiplying the utility level (information obtained in phase 1) with the number of years and individual lives with the condition.

Health economic evaluation studies are frequently characterized by degrees of uncertainty or methodological considerations. In the current study, one-way, multi-way and probabilistic (monte carlo/non-parametric bootstrapping) sensitivity analyses will be conducted to handle various uncertainties. Uncertainty analyses will be expressed in terms of cost-effectiveness acceptability curves.

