Drop-outs are unlikely to be a large problem since there will be only one study visit complemented by the collection of follow-up information.

We will analyse the whole population for the primary analysis and perform a sensitivity analysis excluding the low recruiting practices (less than 10 patients recruited for 12 months) to avoid our results to be susceptible to selection bias. In previous trials this resulted in approximately 10% of practices.

Practices that do not recruit children at all will be stopped after the first two monitoring visits and replaced by new practices to avoid reducing the total number of clusters available for analysis.

The percentage of missing data for the primary outcome of antibiotic prescribing proportion is expected to be low as this will be registered at the first contact consultation. In our previous ERNIE2 trial, we found 4% of missing data for the primary outcome of antibiotic prescribing proportion. Multiple imputation will be considered for the primary outcome measure as well as missing values for patient-reported outcomes (if there are any). Other outcomes will be collected from the patient health record of the physician.

Multiple imputation will be applied to deal with missing data. Imputation will be performed for the binary outcome variable and logistic regression will be used as imputation model. Predictors for the imputation model are baseline patient characteristics and intervention.

2. ARON App Data

A substantial drop-out rate in app completion is anticipated, with non-completion of the app not considered grounds for exclusion from the study. To address this, proactive measures were introduced to enhance participation rates, such as the provision of information about the smartphone app and instructions on installation to children and their parents during the baseline consultation. Additionally, the app was made available in three languages (Dutch, French, English).

Multiple imputation will be applied to deal with missing data. For imputation of continuous variables, a linear regression model will be employed, with baseline patient characteristics and intervention serving as predictors for the imputation model.

3. Administrative Data

Multiple imputation, following Rubin's rules, will be utilized to address missing data. Predictors for the imputation model will include baseline patient characteristics and the intervention.

4. Interview Transcripts

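### Protocol 11.4 fills missing costs by single imputation while the SAP uses multiple imputation; the protocol rule makes intervals too narrow for cost components with material missingness

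*Protocol*

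**What the plan says.** Protocol 11.4, Part II, raises the problem of missing cost data and settles on one method: "In the current research project, single imputation methods will be used". It explains that "the missing data are replaced with a single predicted value (e.g. the adjusted mean value"). The safeguard offered is: "Sensitivity analyses will be conducted to determine how different input values will impact the outcome". The same section plans non-parametric bootstrapping and cost-effectiveness acceptability curves.

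The SAP section on handling missing values sets rules by data source. For the administrative data: "Multiple imputation, following Rubin's rules, will be utilized to address missing data". For the app data it also prescribes multiple imputation, adding: "For imputation of continuous variables, a linear regression model will be employed". For REDCap it prescribes multiple imputation with a logistic model for the binary outcome. Rubin's rules are named for the administrative data (and, elsewhere in the SAP, for the primary endpoint), but not in the app paragraph. On completeness of the app the SAP says: "A substantial drop-out rate in app completion is anticipated".

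These sources feed the costs. Under Protocol 11.4 and the SAP's Data Source section, insurance-number linkage supplies hospitalisation and reimbursed drugs, and the app supplies resources that the health record does not capture. The SAP's cost-effectiveness section has no imputation rule of its own. Its closing section on deviations from the pre-specified plan records none.

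**The concern.** The documents give two different rules for the same data, and neither says which prevails. The choice matters because deterministic single imputation does two things at once. It places filled-in values exactly on the prediction, which shrinks the sample variance, and it leaves the sample size at its full value as though those children had been observed. Standard errors and p-values for cost differences then look more precise than the data allow. A bootstrap that resamples a dataset imputed once inherits the fault, and so would acceptability curves built that way. Varying input values in a sensitivity analysis does not put back the missing variance.

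**Working it through.** **The plan's own figure.** The only number attached to the cost analysis is about 3,056 children per group (Protocol 11.4). It follows from Protocol 11.1.1. With rates 30.43% and 22.65%, 50 patients per cluster, ICC 0.063, two-sided alpha 0.05 and 90% power:

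- n per arm = (1.960 + 1.282)² × [0.3043×0.6957 + 0.2265×0.7735] × [1 + 49×0.063] / 0.0778² ≈ 2,745, i.e. 54.9 and so 55 clusters of 50, or 5,500 children in total.
- 5,500/0.9 = 6,111, and 6,111/2 ≈ 3,056.

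The figure reproduces, but from the superseded total; the current 7,000 implies 3,500 per group. This does not matter below, because n cancels.

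**Inputs not in the documents.** No missing share for costs is given. I take f from 4% to 50%. The lower end is the 4% missing that the SAP reports for a different outcome, antibiotic prescribing in the earlier trial. R², the share of cost variance explained by the imputation model, is assumed to lie between 0 and 0.5. Data are taken as missing completely at random.

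**Single component, weak model.** With S the cost SD, n per arm and R² = 0:

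- reported SE = S·√((1−f)/n)
- true SE = S/√(n(1−f))
- ratio = 1−f, and coverage = 2Φ(1.96(1−f)) − 1

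| f | reported/true SE | coverage of nominal 95% CI |
|---|---|---|
| 4% | 0.96 | 94.0% |
| 10% | 0.90 | 92.2% |
| 20% | 0.80 | 88.3% |
| 30% | 0.70 | 83.0% |
| 50% | 0.50 | 67.3% |

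**Model with some predictive value.** Filled-in values now carry variance R²S², so ratio = √[(1−f+fR²)(1−f)/(1−fR²)]. At f = 30% and R² = 0.3: √[(0.79×0.70)/0.91] = 0.78, coverage 87%. At R² = 0.5 the ratio is 0.84, coverage 90%.

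**Total cost, only the app part missing.** Let w be the app share of total-cost variance (an assumption), with independent components and R² = 0. Then ratio = √{[1−w+w(1−f)]/[1−w+w/(1−f)]}. At f = 40%:

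- w = 10%: √(0.96/1.067) = 0.95, coverage about 94%.
- w = 30%: √(0.88/1.20) = 0.86, coverage about 91%.
- w = 100%: 0.60, coverage 76%.

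**Simulation.** In 1,000 trials per setting with skewed (gamma) residual costs, 3,056 per arm and R² = 0.1, single imputation gave a reported/true SE ratio of 0.74 and coverage of 86% at f = 30%, and 0.53 and 70% at f = 50%. Multiple imputation with ten datasets and Rubin's rules, across all settings run, gave ratios of 0.97 to 1.02 and coverage of 94.5% to 96.6%. With 61 clusters of 50 per arm and a cluster-level analysis, the single-imputation ratio at f = 30% was 0.68 (ICC 0.025) and 0.69 (ICC 0.063), so clustering barely changes the factor. Bootstrapping data imputed once gave 0.72 of the spread obtained when imputation was repeated in each resample (f = 30%).

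**The case against.** The strongest reply is that the SAP already has the better rule. It is the more detailed document and presents itself as the guide to the final analysis, while Protocol 11.4 only sketches an economic analysis that it describes as outside the trial and conditional on the effectiveness results. Much of this stands: harm arises only if the analyst follows the protocol. But both documents list cost-effectiveness as an exploratory endpoint, the SAP schedules the work, and neither gives the SAP precedence or acknowledges the change.

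A reader might infer that all cost results lose precision in direct proportion to the missing share, so that substantial app drop-out takes total-cost coverage to something like 76%. The documents do not support that. Proportionality needs an imputation model that explains nothing, and the protocol's own example is an adjusted mean. It also needs the whole cost to be missing, whereas linkage covers most direct costs for every child with a valid insurance number, and the protocol chose this complementary approach to limit missing data.

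A reader might also infer that the acceptability curves will certainly be overconfident. Neither document says whether imputation comes before the bootstrap or is repeated within it, so that is a risk left open and not an established fault.

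Finally, the SAP rule is not beyond question. Its named predictors are baseline characteristics and intervention, with no practice term, and it uses a linear model for continuous app variables although costs are usually skewed. That bears on how the rule is written out; it does not favour single imputation.

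**Conclusion.** The inconsistency is real, and the protocol rule is wrong as written. For a cost component with material missingness it understates uncertainty: by about 10% of interval width at f = 10% and 30% at f = 30% if the model predicts little, and by about 22% at f = 30% if R² = 0.3. For total cost the loss is much smaller unless app costs dominate the variance. At 4% missing it is negligible.

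These sizes rest on assumed values of f, R² and w and on data missing completely at random. They are most relevant to costs recorded only in the app, where the SAP itself expects substantial non-completion. It would go too far to read this as a threat to the trial's main conclusions: the primary and secondary outcomes do not use the rule.

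**What to change.** In Protocol 11.4, replace the single-imputation sentences with multiple imputation combined by Rubin's rules for all cost and resource-use variables, app costs included. State in the SAP that Rubin's rules apply to the app data too, and record the change from the protocol in its deviations section. Repeat the imputation within each bootstrap resample, or carry the imputation variance into the acceptability curves by another stated method. While editing, say how the imputation model treats practice and skewed costs, and update the 3,056 per group.

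The cost is wording and some computing time; no new data are needed. Cost intervals will be wider than the protocol rule would show, by an amount that depends on the share missing. For a single component with a weak model the factor is 1/(1−f), i.e. 1.11 at 10% and 1.43 at 30%; it is less for total cost.

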12 DATA HANDLING

12.1 Data collection tools and source document identification

Data collection will be performed through REDCap, an electronic data capture software. This tool allows for secure, encrypted and pseudonomysed data transfer from multiple sources into a central database. Data can be collected continuously or in a one-time fashion depending on the resource. REDCap is a secure web application for building and managing online databases. REDCap is specifically geared to support online data capture for research studies.

12.2 Data handling and record keeping

REDCap stores its data and all system and project information in various relational database tables (i.e. utilizing foreign keys and indexes) within a single MySQL database. All project data is stored and hosted at our institution, and no project data is ever transmitted at any time by REDCap from our institution to another institution or organization.

12.3 Access to Data

REDCap has a built-in audit trail that automatically logs all user activity and logs all pages viewed by every user, including contextual information (e.g. the project or record being accessed). Whether the activity be entering data, exporting data, modifying a field, running a report, or add/modifying a user, among a plethora of other activities, REDCap logs all actions. The logging record can itself be viewed within a project by users that have been given privileges to view the Logging page. The Logging page allows such users to view or export the entire audit trail for that project, and also to filter the audit trail in various ways based upon the type of activity and/or user. The built-in audit trail in REDCap allows administrators to be able to determine all the activity and all the data viewed or modified by any given user.

12.4 Archiving

The Sponsor is responsible for archiving study specific documentation (such as but not limited to protocol, potential amendments and final report) for at least twenty years. Destruction of essential documents will require authorization from the Sponsor.

13 MONITORING, AUDIT & INSPECTION

The investigator will permit trial-related monitoring, and audits, providing direct access to all related documents.

Electronic CRFs, including progress notes and copies of laboratory and medical test results must be available at all times for review by the sponsor's clinical trial monitor and auditor. The accuracy of the data will be verified by review of these documents.

For all details about monitoring, we would like to refer to the Trial Monitoring Plan, which will be developed and agreed by the Trial Management Group (TMG) and TSC based on the trial risk assessment.

14 ETHICAL AND REGULATORY CONSIDERATIONS

14.1 Ethics Committee (EC) review & reports

The study will be conducted in compliance with the principles of the Declaration of Helsinki (current version), the principles of GCP and in accordance with all applicable regulatory requirements. This protocol, the informed consent forms and other related documents e.g. advertisements and physician information letters, will be submitted for review to the Research Ethics Committee (REC) and to the Sector Committee for Social Security and Health of the Privacy Commission.

Any subsequent protocol amendments will be submitted to the REC and Sector Committee for approval. No substantial amendment that require review by REC will be implemented until the REC grants a favourable opinion for the study.

The study can and will be conducted only on the basis of prior informed consent by the parents or legal guardian of the study participants, to participate in the study. Extensive discussion of risks and possible benefits of participation will be provided to the patients and/or their families. The participating physician shall obtain a signed informed consent form for all study participants prior to their enrolment and participation in the study in compliance with all

applicable laws, regulations and the approval of the (local) Ethics Committee, if required. The research facility shall retain such ICFs in accordance with the requirements of all applicable regulatory agencies and laws.

All correspondence with the REC shall be retained in the Trial Master File/Investigator Site File.

The Chief Investigator acknowledges that it is his responsibility to produce annual progress reports (APR) and he will do so by submitting to the REC within 30 days of the anniversary date on which the favourable opinion was given, and annually until the study is declared ended.

The Chief Investigator shall notify the REC of the end of the study. Should the study be ended prematurely, the Chief Investigator will notify the REC and include the reasons for the premature termination. The Chief Investigator will submit a final report with the results, including any publications/abstracts, to the REC.

14.2 Peer review

Peer review will be conducted by expert referees to the professional and scientific standards expected for clinical studies.

14.3 Public and Patient Involvement

We will present the suggested intervention to parents and children to receive input on potential barriers and facilitators of our proposed trial.

Furthermore, patient representative groups will be contacted to obtain useful feedback regarding our trial.

As we are currently involved in several paediatric studies, we are in the process of setting up a standing patient panel to advise on all ongoing projects. This would encompass:

- communicating and engaging with parents through co-design workshops at the pilot phase to ensure that research process accurately address the needs of the parents
- individual interviews with the parents will be carried out alongside the trial to ensure that the research outputs reflect the underpinning barriers and facilitators to intervention uptake, increasing their opportunity to benefit.
- we will ask them to assess any patient facing material that will be produced, such as patient information sheets, and ask for their feedback on readability and content.
- we will also ask for advice on how to disseminate our findings to a lay audience.
- the principal investigator will be appointed PPI co-ordinator and will liaise with the group during study set up, recruitment and dissemination phases.
- they will be reimbursed for their time, travel and childcare expenses.
- the PI will make sure the results of the panel discussion will be passed on to the steering committee of the study.

14.4 Regulatory Compliance

This protocol and other related documents will be submitted for review to the Sector Committee for Social Security and Health of the Privacy Commission.

This study protocol and the conduct of the study in general is in compliance with applicable law, including but not limited to the Belgian law of 7th May 2004 regarding experiments on the human person and any relevant amendments.

14.5 Protocol compliance

The Chief Investigator is responsible for ensuring that the clinical study is performed in accordance with the protocol, current ICH guidelines on GCP, and applicable regulatory and country-specific requirements. GCP is an international ethical and scientific quality standard for designing, conducting, recording, and reporting studies that involve the participation of human subjects. Compliance with this standard provides public assurance that the rights, safety, and well-being of study participants are protected, consistent with the principles that originated in the Declaration of Helsinki, and that the clinical study data are credible.

It is acknowledged and agreed that prospective, planned deviations or waivers to the protocol are not allowed under applicable regulations on clinical studies and must not be used. However, should there be an accidental protocol deviation, such deviation shall be adequately documented on the source documents and on the relevant forms and

reported to the Chief Investigator and Sponsor immediately. Protocol deviations which are found to frequently recur, will require immediate action. Chief Investigator acknowledges that such recurring protocol breaches could be potentially classified as a serious violation (as defined under section 13.6).

14.6 Notification of Serious Breaches to GCP and/or the protocol

It is understood that "a serious violation" is likely to effect to a significant degree

- □ the safety or physical or mental integrity of the participants of the study; or
- □ the scientific value of the study

The Sponsor shall be notified immediately upon becoming aware of a serious violation during the study conduct phase. The Sponsor shall notify the licensing authority in writing of any serious violation of the conditions and principles of GCP in connection with that study; or the protocol relating to that study, as amended from time to time, within 7 days of becoming aware of that violation.

14.7 Data protection and patient confidentiality

The study will be conducted in compliance with the requirements of the Belgian Privacy Act of 8 December 1992 on the protection of privacy in relation to the processing of personal data and the European Data Protection Act. Any collection, processing and disclosure of personal data, such as patient health and medical information is subject to compliance with the aforementioned personal data protection laws.

Any personal data shall be treated as confidential at all times including during collection, handling and use, and that the personal data (including in any electronic format) shall be stored securely at all times and with all technical and organizational security measures that would be necessary for compliance with data protection legislation. The Sponsor shall take appropriate measures to ensure the security of all personal data and guard against unauthorized access thereto or disclosure thereof or loss or destruction while in its custody.

The personal data of study participants will be encoded, which means that they can only be related to an identifiable person by means of a unique code. The unique code will only be in the possession of the members of the study team who are in direct contact with the study participants. In no event will the coded personal data include personal identifiers, including any Study participant's initials. Such coded personal data can only be traced or linked back by said study team members and said study team members shall treat these codes as strictly confidential.

Only anonymized personal data will be disclosed to KCE or, where specifically requested by KCE, coded personal data. In no event shall any of the reports, documents, information disclosed to KCE include data that may be linked to the specific identity of a study participant. The Sponsor shall make sure that the key to personal identities of all persons to whom the data relates is kept in a separate and secure place in compliance with applicable data privacy legislation and shall not be disclosed to KCE or unauthorized persons.

All study related data and documents will be stored for twenty (20) years, in accordance with Belgian legislation.

14.8 Financial and other competing interests for the chief investigator, PIs at each site and committee members for the overall trial management

The Chief Investigator hereby declares having no financial arrangement whereby the value of the compensation for conducting the study could be influenced by the outcome of the study; not having received any significant payments of other sorts from the Sponsor, such as a grant to fund ongoing research, compensation in the form of equipment, retainer for ongoing consultation, honoraria, ownership interest that may be related to products, services or interventions considered for use in the study, or that may be significantly affected by the study; having no commercial ties with any pharmaceutical, behaviour modification, and/or technology company; nor having any non-commercial potential conflicts e.g. professional collaborations that may impact on academic promotion.

In consideration of participation in the study, the nominated payee will receive the sums set out in the payment schedule attached to the clinical trial agreement.

